### 3.9. Study Procedures

Subjects will be enrolled at approximately 65 sites in the United States and Canada. Each subject will receive study drug once daily, in a tablet formulation, for 14 days. It is anticipated it will take 12 months to complete enrollment and 13 months to complete the entire study.

**Table 1: Schedule of Assessments**

Visit	Screening	Visit 1	Visit 2	Visit 3	Safety Follow-up
Study Day	Day -28 to Day -1	Baseline (Day 0)	Day 7	Day 14	Day 21
Window			±1 day	±1 day	±1 day
Informed consent	X				
Demographic information	X				
Medical History and Disease History	X				
Virology/Serology a	X				
Inclusion/exclusion criteria	X	X			
Physical examination	X	X		X	X
Vital signs b	X	X	X	X	X
ECG	X	X c	X c	X c	X
Hematology d	X	X		X	X
Serum chemistry d	X	X		X	X
Pharmacokinetic sample e		X	X	X	
Urinalysis d	X	X		X	X
Pregnancy test f	X	X	X	X	X
UDS g	X	X	X	X	
Nocturnal overnight PSG h		X	X	X	
MWT i		X	X	X	
CGI-S j		X	X	X	
CGI-C j			X	X	
ESS k	X	X	X	X	
C-SSRS k	X	X	X	X	X
PGI-C k,l		X	X	X	
Diary dispensing m	X	X	X	X	
Washout from EDS/cataplexy medications n	X				
Assign/randomize to IP		X			

This document is confidential.

**Statistical Analysis Plan**

Sponsor: Suven Life Sciences; Protocol No.: CTP2S13031H3

Visit	Screening	Visit 1	Visit 2	Visit 3	Safety Follow-up
Study Day	Day -28 to Day -1	Baseline (Day 0)	Day 7	Day 14	Day 21
Window			±1 day	±1 day	±1 day
Dispense IP		X	X		
Collect IP o			X	X	
IP accountability o			X	X	
Prior medications/concomitant medications o,p	X	X	X	X	X
AEs including AESIs o,p	X	X	X	X	X

Abbreviations: AE, adverse event; AESI, adverse event of special interest; CGI-C, Change in Clinical Global Impression of Change; CGI-S, Clinical Global Impression of Severity; C-SSRS, Columbia Suicide Severity Rating Scale; ECG, electrocardiogram; ESS, Epworth Sleepiness Scale; IP, investigational product; MWT, Maintenance of Wakefulness Test; PGI-C, Patient Global Impression – Change; UDS, Urine Drug Screen.

- a Virology and Serology laboratory tests (i.e., Hepatitis B, Hepatitis C, and human immunodeficiency virus) will be completed at Screening.
- b Vital signs (i.e., SBP, DBP, body temperature, pulse, and respiratory rate) to be obtained after subject has been sitting for at least 5 min. The method of obtaining body temperature will be per sites standard practice but should be obtained by the same method for a given subject throughout the study. Vital signs may be collected prior to the PSG and the first MWT.
- c Electrocardiograms should be obtained after the subject has been quiet and supine for approximately 3 minutes. An ECG will be captured at baseline (Day 0, Visit 1), and 3 h (±30 min) post dose on Days 7 and 14.
- d Laboratory assessments are listed in protocol Table 2.
- e Venipuncture for point estimates of the plasma concentration of SUVN-G3031 will be obtained at baseline (Day 0; blank), and on Day 7 (Visit 2) and Day 14 (Visit 3) at the estimated trough just prior to dosing and at the estimated maximum plasma concentration of SUVN-G3031 (3 ± 0.5 hours post dosing on Day 7 and Day 14) for a total of 5 samples.
- f A serum pregnancy test will be completed at baseline (Day 0; Visit 1). Urine pregnancy tests will be completed at Screening, Baseline (Visit 1), Day 7 (Visit 2), Day 14 (Visit 3), and Day 21 (Safety Follow-up visit).
- g A positive UDS at Screening can be repeated up to Day -1; however, a negative UDS is required prior to Day 0 (Baseline visit), and a second negative UDS is required on Day 0 (Baseline visit).
- h Within the current study nocturnal overnight PSG will be completed at baseline (Day 0; Visit 1), Day 7 (Visit 2), and at Day 14 (Visit 3). Variables to be collected will include latency to persistent sleep in minutes (latency from lights-off to the first epoch of 20 consecutive epochs of any stage of sleep), number of arousals, number of awakenings, sleep efficiency, total sleep time in minutes, wake after sleep onset in minutes, percentage of time in stage 1, 2, 3, 4, REM sleep percentage, REM sleep latency in minutes and periodically movements during sleep (N).
- i The [REDACTED] MWT will be utilized within this study and will be performed after a nocturnal overnight PSG at baseline (Day 0), Day 7, and at Day 14 according to validated standards. The MWT will begin at approximately 2 hours after awakening (4 total MWT sessions will be performed at 2 hour intervals). Subjects will be required to recline in a quiet, dimly lit bedroom and instructed to remain awake for as long as possible. Each MWT session will be stopped after the onset of sleep or after [REDACTED] if sleep did not occur. The onset of sleep will be evaluated using a standard PSG montage and defined as 3 consecutive 30-second epochs of stage 1 sleep or 30 seconds of sleep stage 2, 3, 4, or rapid eye movement sleep.
- j Physicians will complete a CGI-S and CGI-C assessments for EDS rather than totally of illness. The CGI-S assessment will be completed first followed by CGI-C evaluation. The administrator of the CGI-S and CGI-C should remain consistent for each subject at each visit.
- k ESS, PGI-C, C-SSRS assessments will be completed in this order at the beginning of each evaluation day prior to start of first MWT session. Note: 2 distinct forms of C-SSRS will be used: "Baseline-Screening" form will be used at Screening and "Since Last Visit" form will be used at subsequent visits.

This document is confidential.

**Statistical Analysis Plan**Sponsor: Suven Life Sciences; Protocol No.: CTP2S13031H3

---

- l For the PGI-C, the subject will be asked to address the totality of experience on study medication, without attempts to demarcate between excessive daytime somnolence versus cataplexy.
- m Sleep diary is collected nightly by the subject from Screening through Visit 3. The subject will provide the sleep diary from the preceding week at the beginning of each visit. In addition, dosing data will be collected in the diary.
- n Washout period will occur within a maximum 28-day Screening period to allow for minimum drug free period of  $\geq 7$  days for all stimulants targeting EDS, and  $\geq 14$  days for all agents targeting cataplexy prior to randomization and baseline (Day 0) assessments.
- o At the start of each visit as indicated, the subject will return IP that has not been used, provide sleep diary, report any modification in concomitant medication dosage or regimen, and research personnel will complete a nondirected inquiry for the detection of AEs. Safety assessments completed by the Investigator precede the efficacy assessments.
- p Concomitant medications and AEs may be collected prior to the PSG and the first MWT.

## **4. Study Endpoints**

### **4.1. Primary Efficacy Endpoint**

- Primary endpoint: Change from baseline in the mean total ESS score at Day 14

### **4.2. Secondary Efficacy Endpoints**

- Change from baseline in the mean CGI-S score related to EDS at Day 14
- Change from baseline in the mean MWT score at Day 14

### **4.3. Exploratory Endpoints**

- Change from baseline in the mean total ESS score at Day 7
- Change in MWT score, within each of the 4 MWT sessions within a single day (Day 7 and Day 14)
- Proportion of subjects reporting CGI-C scores of 1 or 2 at Day 7 and Day 14 (EDS)
- Proportion of subjects reporting CGI-C scores of 1 or 2 or 3 at Day 7 and Day 14 (EDS)
- Proportion of subjects reporting CGI-S scores related to EDS of 1 or 2 at Day 7 and Day 14
- Proportion of subjects reporting CGI-S scores related to EDS of 1 or 2 or 3 at Day 7 and Day 14
- Proportion of subjects with improvement in the PGI-C score from baseline to Day 7 and Day 14
- Change from baseline in the behavior of Sleep Diary parameters at Day 7 and Day 14 (7-day average)
- Change from baseline in the mean CGI-S score related to EDS at Day 7
- Changes in the behavior of the nocturnal overnight PSG assessments at Day 7 and Day 14
- Change from baseline in the mean MWT score at Day 7
- Analysis of all endpoints (except Sleep Diary parameters and nocturnal overnight PSG assessments) evaluating SUVN-G3031 doses (2 mg and 4 mg) compared to placebo.

### **4.4. Pharmacokinetic Endpoints**

Not applicable for this study.

The plasma concentration data will be summarized using descriptive statistics and all plasma concentration data will be listed using the PK population.

### **4.5. Pharmacodynamic Endpoints**

No Pharmacodynamic assessments performed for this study.

### **4.6. Safety Endpoints**

- Physical examination
- Vital signs
- Laboratory assessments (blood and urine)
- Electrocardiogram (ECG)
- Adverse events (AEs)
- Adverse events of Special Interest (AESIs)
- Columbia-Suicide Severity Rating Scale (C-SSRS)

**4.7. Health-economics Endpoints**

Not applicable for this study.

**4.8. Other Endpoints**

Not applicable for this study.

## **5. Analysis Population**

### **5.1. Safety Population**

The safety population will include all randomized subjects who receive at least 1 dose of study treatment. The treatment group assignment in this population will be defined by the treatment actually received. This population will be used for the analysis of safety.

### **5.2. ITT Population**

The intent-to-treat (ITT) population will include all subjects who were randomized, received at least one dose of study treatment drug, and had baseline and at least one post-baseline primary efficacy assessment. This population will be used for the analysis of efficacy.

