## 7.2.2 Assessments

### 7.2.2.1 Primary Outcome Measure

The primary objective pivots upon changes in EDS in patients with Na-1 and Na-2. The primary outcome measure, the change in total ESS scores from baseline, is used to derive the primary dependent variable. A successful study requires demonstration of a statistically significant difference between treatment groups based upon the ESS as a single primary endpoint, using a prespecified analytic model and an intent-to-treat (ITT) dataset.

The ESS consists of 8 questions chosen on a priori grounds to represent activities with a wide range of different somnificities.

The ESS is a self-administered questionnaire wherein respondents are asked to rate on a 4-point scale (0–3) their usual chances of dozing off or falling asleep while engaged in 8 different activities (see [Section 11.3](#)). It is important that participants answer every question, as there is no method for interpolating item scores and a missed question results in an invalid test. Most people engage in the activities in the test at least occasionally, although not necessarily every day. The recall period for the test asks subjects to rate experiences taking place “in recent times,” which is purposefully vague and is meant to represent a few weeks to a few months. Within the study, the ESS will be completed weekly, consistent with the recall period. The ESS score (the sum of 8 item scores, 0–3) can range from 0 to 24. The higher the ESS score, the higher the person’s average sleep propensity in daily life, or their “daytime sleepiness.” The questionnaire takes no more than 2 or 3 minutes to answer. The ESS can be interpreted per the bullets below:

- 0 to 5 Lower Normal Daytime Sleepiness
- 6 to 10 Higher Normal Daytime Sleepiness
- 11 to 12 Mild EDS
- 13 to 15 Moderate EDS
- 16 to 24 Severe EDS

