### **8.4 Study Withdrawal, Removal, and Replacement of Patients**

If a patient discontinues study treatment and is withdrawn from the study for any reason, the study site must immediately notify the medical monitor. The date and the reason for study discontinuation must be recorded on the electronic case report form (eCRF). Patients who complete or discontinue early from the study will be asked to return to the study site within 7 days of the last administration of study drug to complete the safety follow-up assessments as indicated in the Schedule of Assessments ([Table 1](#)).

Patients who want to discontinue early from the study (i.e., at the next visit), or who make a decision to withdraw during a scheduled visit, and who remain on study drug should complete

the rating scale/assessments indicated for that visit (Visit 2 or Visit 3) as well as the safety follow-up assessments according to the Schedule of Assessments ([Table 1](#)).

In the event that a patient discontinues prematurely from the study because of a TEAE or serious TEAE, the TEAE or serious TEAE will be followed until it resolves (returns to normal or baseline values) or stabilizes, or until it is judged by the Investigator to no longer be clinically significant.

Once a patient is withdrawn from the study, the patient may not re-enter the study. Care of the patient will return to their usual doctor.

A patient may voluntarily withdraw or be withdrawn from the study at any time for reasons including, but not limited to, the following:

- Unacceptable toxicity or AE.
- Clinically significant abnormal lab values:
  - Alanine aminotransferase (ALT) or aspartate aminotransferase (AST)  $\geq 8x$  upper limit of normal (ULN);
  - ALT or AST  $\geq 3x$  ULN and total bilirubin  $\geq 2x$  ULN at the same visit;
  - ALT or AST  $\geq 3x$  ULN with the appearance of symptoms indicating hepatitis (e.g., worsening fatigue, nausea, vomiting, right upper quadrant pain or tenderness, fever, rash, or eosinophilia).
- QT syndrome, Fridericia's formula corrected QT (QTcF) interval  $\geq 470$  ms (for male subjects) or  $\geq 480$  ms (for female subjects), or torsades de pointes. Abnormal results for ECGs should be confirmed with repeat ECG recordings to ensure reproducibility of the abnormality before withdrawing the subject from the study.
- A positive urinary drug screen at any visit.

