### **14.3 Efficacy Analysis**

All efficacy analyses will be performed using the ITT population.

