#### **14.3.1 Analysis of Primary Efficacy Endpoint**

The primary efficacy endpoint is the change from baseline in the mean total ESS score at Day 14. A successful study requires demonstration of statistically significant differences between the combined SUVN-G3031 doses (2 mg and 4 mg) group and the placebo group at endpoint for the ESS.

The null (H0) and alternative (H1) hypotheses of the study are as follows:

H0: SUVN-G3031 and placebo do not differ in their change from baseline in the mean total ESS score at Day 14.

H1: SUVN-G3031 and placebo differ in their change from baseline in the mean total ESS score at Day 14.

The primary endpoint will be analyzed using a mixed model repeated measures (MMRM) analysis that includes the mean total ESS score from baseline to 7 days through to 14 days. This method is the preferred approach to longitudinal analysis because it utilizes observed data efficiently.

The model will include randomized treatment, visit and treatment-by-visit interaction as explanatory variables, stratification factor for cataplexy patient history (presence or absence) and baseline total ESS score as covariates. The participant effect will be assumed to be random, and an unstructured covariance structure will be assumed for within participant variation. The main comparison will be a contrast between treatment groups at 14 days. Least square mean changes will be estimated for SUVN-G3031 and placebo.

This analysis will be repeated for the ITT and PP populations.

Various sensitivity analyses will be performed using an analysis of covariance (ANCOVA) and multiple imputation pattern mixture model to handle missing data. Estimands specification and sensitivity analyses details will be included in the SAP.

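### The ITT set requires a post-baseline ESS, so patients with no valid ESS at Day 7 or Day 14 are left out of the planned imputation analyses and of the CGI-S and MWT analyses

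*SAP*

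**What the plan says.** SAP 5.2 and Protocol 14.2 define the ITT population in the same way: randomised, at least one dose, and "had baseline and at least one post-baseline primary efficacy assessment". The primary endpoint in SAP 4.1 is "Change from baseline in the mean total ESS score at Day 14", so the qualifying assessment is an ESS. Protocol 14.3 adds: "All efficacy analyses will be performed using the ITT population".

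Under Protocol 8.4, patients who discontinue early are asked "to return to the study site within 7 days of the last administration of study drug to complete the safety follow-up assessments". The Schedule of Assessments places the ESS at Screening and Visits 1, 2 and 3, with no mark under Safety Follow-up. There is one exception. Patients who decide to leave at or for a visit, and are still on drug, should complete "the rating scale/assessments indicated for that visit (Visit 2 or Visit 3) as well as the safety follow-up assessments".

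On incomplete forms, Protocol 7.2.2.1 says that "a missed question results in an invalid test".

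For the primary endpoint, Protocol 14.3.1 plans sensitivity analyses by ANCOVA and a "multiple imputation pattern mixture model to handle missing data", and leaves the details to the SAP. SAP 8.4 analyses CGI-S and MWT on the ITT population, with multiple-imputation versions of the MMRM and ANCOVA as sensitivity analyses and a repeat on the per-protocol set.

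**The concern.** A set that depends on an outcome recorded after randomisation is a modified ITT set. For the primary MMRM this matters little: a patient with no post-baseline ESS adds nothing to the likelihood, whether or not the set includes them.

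The sensitivity analyses are different. Imputation can use a patient who has only a baseline value, and the analyses planned for missing data exist to ask what happens if the missing-at-random assumption fails. Patients who leave in the first week, for intolerance or lack of effect, are those for whom that question is most pressing. The population definition removes them before any imputation begins.

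The secondary endpoints have a further problem. CGI-S and MWT use the same ESS-dependent set. A patient with usable CGI-S and MWT data but no valid post-baseline ESS would be dropped from both, although that patient could have contributed to those MMRMs.

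**Working it through.** **1. The plan's own figure.** Inputs from Protocol 14.1: difference 3.5 on the MWT, SD 5.0, two-sided 0.05, 80% power, 10% dropout.

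- Normal approximation: n = 2(1.960 + 0.842)² × 5.0² / 3.5² = 32.04, so 33 per arm; 33/0.9 = 36.7, so 37.
- Two-sample t: 34 evaluable per arm (power 81.2%); 34/0.9 = 37.8, so 38.

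The stated 38 per arm reproduces and is not in dispute. Only the 10% dropout is carried forward.

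**2. Who falls outside the set.**

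| Patient's course | Post-baseline ESS | In the ITT set? |
|---|---|---|
| Stops before Visit 2, returns for safety follow-up only | None scheduled | No |
| Decides to leave at or for Visit 2, still on drug | Visit 2 ESS | Yes |
| Stops between Visit 2 and Visit 3 | Day 7 ESS | Yes; Day 14 is handled by the model |
| One invalid ESS form, the other valid | One valid | Yes |
| Attends, but no valid ESS at either visit | None valid | No, if an invalid form is not an assessment; the plan does not say |

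**3. How many.** Excluded dropouts = N × 0.10 × s, where s is the share of dropouts who leave before the Day 7 ESS. The documents do not give s, so it is varied over its whole range.

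| s (assumed) | N = 114 | N = 171 |
|---|---|---|
| 0% | 0 | 0 |
| 25% | 2.9 | 4.3 |
| 50% | 5.7 | 8.6 |
| 100% | 11.4 | 17.1 |

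The last row requires every dropout to precede the Day 7 ESS. Patients who stay in the study with no valid ESS at either visit would be additional; the documents give no rate for them.

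**4. What the omission could do to the estimate.** Let f be the fraction of an arm excluded and g the amount by which their mean ESS change would have been worse than that of the retained patients. The mean over all patients in the arm is the retained mean plus f × g, so the retained mean looks better by f × g. With f from 2% to 10% and g from 2 to 5 points (both assumed), one arm shifts by 0.02 × 2 = 0.04 to 0.10 × 5 = 0.5 points.

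The primary contrast pools two equal dose arms against placebo (SAP section 8), so

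net bias = (f₂g₂ + f₄g₄)/2 − f_P g_P,

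where 2, 4 and P denote the 2 mg, 4 mg and placebo arms. If only one dose arm is affected, the range halves to 0.02 to 0.25. If all three arms lose the same fraction with the same gap, it is zero. If placebo loses more, the sign reverses.

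**5. Two rules that do not fit the definition.** SAP 8.1 fills visits after a death with the worst observed value, but a patient who dies before any post-baseline ESS is not in the set. SAP 6.3.2 imputes a missing baseline from the first post-baseline value, while the set already requires a baseline.

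**The case against.** Four stronger readings are tempting, and the documents do not support them.

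- *Anyone who stops drug early gives no ESS.* This is true only of stops before the Visit 2 ESS. Later stoppers have a Day 7 value, and patients who leave at a visit while on drug complete that visit's scales.
- *One skipped ESS item costs a patient their CGI-S and MWT data.* One valid post-baseline ESS keeps the patient in, so both forms must be invalid or missing. Even then, exclusion depends on an invalid form not counting as an assessment.
- *Every imputation analysis is shown to exclude these patients.* SAP 8.2 and 8.3 are not in the public text, and under Protocol section 14 the SAP prevails where the two differ. For the primary endpoint, the exclusion is inferred from the ITT definition and the general rule in Protocol 14.3.
- *The drug is flattered by up to half an ESS point.* That is a one-arm figure on assumed inputs. It shrinks in the pooled contrast and placebo losses can offset it.

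Other points in the plan's favour also stand. Under missing-at-random imputation, a baseline-only patient adds almost nothing, so restoring them matters mainly where the pattern-mixture model departs from that assumption; the imputation rule is not visible. Protocol 5.2.2 reports no discontinuations for adverse events among 72 healthy volunteers, so early losses may be few. The exclusions will be visible: SAP 7.1 summarises membership of each population with reasons for exclusion, and Listing 16.2.3 lists them.

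Reporting who was excluded is not the same as testing whether their exclusion matters. That part of the concern remains.

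**Conclusion.** The concern holds in a limited form. Patients with no valid ESS at Day 7 or Day 14, notably those who stop drug before the Visit 2 ESS, are outside the ITT set. On the visible text, they are therefore also outside the imputation analyses meant to handle missing data. The text supports this directly for the secondary endpoints and by inference for the primary. The loss of valid CGI-S and MWT data is a rarer case and depends on how an invalid ESS form is classified.

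At 10% dropout the number is 0 to 11 of 114, or 0 to 17 of 171; the timing of dropout decides where in that range it falls. The net direction of bias is unknown, and the bias figures in the working are illustrations. The primary MMRM estimate is not in question. The change is worth making because it is cheap and lets the sensitivity analyses address the patients with no outcome data.

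**What to change.** 1. Define ITT as all randomised patients, or all randomised and dosed patients, and keep the primary MMRM on available data. The primary estimate stays essentially unchanged; a death before the first post-baseline ESS is the exception, because the worst-value rule could then apply.
2. Run the multiple-imputation and pattern-mixture sensitivity analyses on all such patients with a baseline ESS, including those with no post-baseline value.
3. For CGI-S and MWT, base inclusion on that endpoint's own data, without reference to ESS.

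The cost is SAP wording and possibly a slightly less favourable sensitivity estimate. No new data are needed.

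Adding an ESS at safety follow-up is not recommended. It would need a protocol amendment and, since SAP 3.6 shows the interim analysis has already taken place, would reach only later patients. It would also give an off-drug value of unclear use.
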